**Twenty (20) subjects will begin low dose tacrolimus with concentration controlled everolimus (treatment arm)**

Tacrolimus will be initiated according to our practice. In this treatment arm, the Tacrolimus dose will be adjusted from day 3 on, to a target whole blood trough concentration of 4 ng/mL to 7 ng/mL. From month 2 until Month 6, the target Tacrolimus trough level will be 3 ng/mL to 6 ng/mL. After month 6, the Tacrolimus dose should be adjusted in order to achieve a target trough level of 2 ng/mL to 5 ng/mL.

From day 5 on, the starting dose of Everolimus (0.75 mg bid) will be increased if the trough level is < 3 ng/mL, or reduced if the trough level is > 8 ng/mL.

All drugs will be administered in an open label fashion.

The following transplant recipient data will be collected at the time of randomization:.  
Demographics: Age at transplantation, sex and race.

Causes of end-stage renal disease

Transplant related information: donor age, histocompatibility and cross match data, viral serology, history of acute rejection and delayed graft function, use of ACEI and/or ARB, level of renal allograft function - estimated GFR ( e-GFR(12) using MDRD formula, proteinuria.

Blood samples will be obtained prior to randomization from all renal transplant recipients for baseline T and B cell functional activity and characterization of the cell subpopulations by flow cytometry.

-All recipients will be routinely followed at our Transplant center with post-transplant labs (SMA7, CBC, and relevant immunosuppression trough levels).

Additional blood will be collected and analyzed for the study at 3, 6, 12, 24 and 36 months post-randomization. If the final blood sample cannot be drawn at the 36 month timepoint, it may be drawn up to 50 months post-transplant. These samples will be used to investigate the impact of the two maintenance immunosuppressive regimens on subpopulation of T cells in comparison with baseline levels. Specifically,

---

we will look at regulatory T cells (Treg: Foxp3+CD4+ CD25bright+) that could have been generated via the two maintenance immunonousuppressive regimens, and correlate the generation of with their function.

RNA from peripheral blood will be also collected and stored for post-hoc analyses of T and B-cell immunoresponse gene expression via gene arrays.

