**Statistical analysis:**

The primary endpoints of the study are graft function and subpopulations of T cells, including regulatory T cells and B cell subpopulations at 3, 6, 12, 24 and 36 months post kidney transplant. The secondary endpoints of the study include 1) incidence of acute rejection, graft loss, and death at 12, 24 and 36 months post kidney transplant; 2) allograft immunohistopathology and gene expression profiles at 12 and 24 months post kidney transplant.

We will run univariate and bivariate analyses for all variables prior to our main analyses. We will evaluate continuous variables using t-tests or F-tests and categorical variables using  $\chi^2$ . We will examine data distributions and test all variables for linear relationships or non-linear relationships.

Descriptive statistics (means, standard deviation, frequency) and correlations (both Pearson and Spearman) among variables will be calculated for preliminary data assessment.

Necessary transformation and imputations will be carried out based on the raw data distribution.

As missing data are inevitable in a longitudinal study, we will determine whether missing data are MCAR (data are missing completely at random), MAR (data are missing at random), or NMAR (not missing at random). If missing data are MCAR or MAR, it is likely that the standard multivariate computations using PROC MI (multiple imputations) will not result in biased standard error estimates. However, if missing data are NMAR, we will use the "pattern mixture" approach to compute a weighted average of the parameters that are associated with the missing data to estimate what the data would have been.

For the primary objective, we hypothesize that subjects receiving low dose CNI with mTOR inhibitor (Everolimus) will exhibit significantly greater graft function and higher numbers of regulatory T cells as compared to the standard dose CNI+MMF group.

We will utilize both repeated-measures ANOVA and random mixed effect models to compare the trajectory change in graft function and proportion of regulatory T cells over 12, 24 and 36 months between the two experimental groups. The method of estimation will be maximum likelihood (ML).

---

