A variety of covariance structures (first order regressive, compound symmetry, Toeplitz, variance components, unstructured) will be carefully examined and compared using the best fitting statistics, such as Akaike's Information (AIC) and Bayesian Information Criteria (BIC). These statistics are likelihood functions and can be compared across models. If, in spite of randomization, distributions of subjects' baseline characteristics are found to be different between the two experimental groups, these variables will be entered as covariates in the statistical analysis.

For the secondary endpoints, we will use logistic regression, Kaplan-Meier method, and Cox proportional hazards models to analyze time-to-event outcomes (acute rejection, graft failure, and death). For allograft immunohistopathology and gene expression profile outcomes, we will first develop a comprehensive immune profile of each participant by longitudinal analysis of frequency and function of T and B cell subsets. We will examine how these correlate with immunohistopathology and alloantibody production using Pearson or Spearman correlations. We will compare correlation coefficients between the two experimental groups using Z -tests to determine the distinct effects of each treatment arm. We will also compare the trajectory changes in cell populations and antibody production over 12, 24 and 36 months using both repeated measures ANOVA and random mixed effect models. All tests will be two-sided, and an error rate of  $\alpha < 0.05$  will be considered statistically significant. All data analyses will be performed using SAS 9.2 statistical software (SAS Inc., Cary, NC).

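### Primary mixed models use ML with no small-sample correction (about 6% type I error instead of 5% with an ordinary F reference), and marker baselines are adjusted for only if the arms differ

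*Combined protocol and SAP*

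**What the plan says.** Under Statistical analysis, the primary comparison uses repeated-measures ANOVA and mixed models to "compare the trajectory change in graft function and proportion of regulatory T cells over 12, 24 and 36 months" between the arms. For estimation: "The method of estimation will be maximum likelihood (ML". The covariance structure is to be chosen by AIC and BIC from five candidates ("first order regressive, compound symmetry, Toeplitz, variance components, unstructured"). Tests are two-sided at 0.05 in SAS 9.2. The section names neither REML, nor a reference distribution, nor a small-sample correction.

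The only covariate rule is conditional: if "baseline characteristics are found to be different between the two experimental groups, these variables will be entered as covariates". It gives no threshold and no list of variables.

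The treatment-arm part of Study design says "Blood samples will be obtained prior to randomization from all renal transplant recipients for baseline T and B cell functional activity", and describes the later samples as showing the "impact of the two maintenance immunosuppressive regimens on subpopulation of T cells in comparison with baseline levels". Sample size and power refers to a change in the Treg percentage. No model term for baseline is specified anywhere.

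**The concern.** Two separate points arise.

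**(a) Size of the primary test.** ML divides the residual sums of squares by N rather than N − 2, so standard errors are too small. With unstructured covariance, an F reference on N − 2 degrees of freedom also makes too little allowance for estimating the covariance matrix. In a trial of 40 both effects are visible, and both push towards false positives. The repeated-measures ANOVA is not affected by ML, but the plan does not say which of the two analyses decides.

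**(b) Baseline adjustment.** Whether a baseline covariate is worth including depends on its correlation with the outcome, not on chance imbalance between randomised arms. A rule triggered by imbalance gives up precision in most trials, and without a criterion it lets the adjusted set be picked after the data are seen.

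Nothing is claimed under (b) for graft function. Study design lists "level of renal allograft function - estimated GFR" among data collected at randomisation, but randomisation is at enrolment and, according to Population, some randomised recipients were withdrawn before dosing for surgical complications. A pre-randomisation eGFR of the graft is therefore not available.

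**Working it through.** **Inputs.** 20 per arm (Study design); 10% attrition at 12 months (Sample size and power), so 20 × 0.9 = 18 per arm and N = 36; three visits, so q = 2 numerator df; ν = N − 2 = 34; α = 0.05 two-sided. The ordinary F reference is an assumption, because the plan states none.

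**Check on n.** A two-sample t-test with 18 per arm has power 0.830 at effect size 1.0 and 0.9999 at 2.0, against the stated 0.82 and 0.99. With 20 per arm the first figure would be 0.869. The plan's own power therefore fits 18 per arm.

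**(a) Exact size, complete normal data**

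- *Unstructured, ML.* The REML-based T² is distributed as [νq/(ν − q + 1)] × F(2, 33), and the ML Wald F equals T² × N/(νq) = (36/33) × F(2, 33). The 5% point of F(2, 34) is 3.276. Size = P(F(2, 33) > 3.276 × 33/36 = 3.003) = **6.3%**.
- *Unstructured, REML, same reference.* P(F(2, 33) > 3.276 × 33/34 = 3.180) = **5.5%**.
- *Compound symmetry, ML.* The 5% point of F(2, 68) is 3.132. P(F(2, 68) > 3.132 × 34/36 = 2.958) = **5.9%**.
- *Single contrast, ML.* P(|t34| > 2.032 × √(34/36) = 1.975) = **5.6%**.

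At 20 per arm the three ML figures are 6.2%, 5.8% and 5.6%. With a chi-square reference at 18 per arm they would be worse: 7.9% unstructured and 6.6% compound symmetry.

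**Size after AIC/BIC selection.** 100,000 simulated trials for each of three assumed covariances: compound symmetry 0.6; autoregressive 0.7 per year; the latter with SDs 1, 1.3 and 1.6. Monte Carlo SE is about 0.08 points. Assumed df: 34 for unstructured, 68 for the others.

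| Analysis | AIC | BIC |
|---|---|---|
| ML | 6.2–6.5% | 6.1–6.5% |
| ML, 34 df for every structure | 5.6–6.3% | 5.4–6.1% |
| REML with Kenward-Roger | 5.1–5.5% | 5.2–5.4% |

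Prespecified unstructured covariance with REML and Kenward-Roger gives 5.0%.

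**Size with dropout.** 20 per arm started; monotone loss completely at random; unstructured; direct likelihood with 34 df for ML; 20,000 trials per covariance; SE about 0.18 points. The rates are assumptions.

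| Missing at 12/24/36 months | ML | REML with Kenward-Roger |
|---|---|---|
| 10/15/20% | 6.6–6.7% | 5.0–5.1% |
| 10/20/30% | 7.2–7.3% | 5.0–5.3% |

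**(b) Covariate rule.** With equal SDs and baseline–follow-up correlation r, the large-sample ratio of the adjusted to the unadjusted interval is √(1 − r²) against follow-up values and √((1 + r)/2) against change scores. At r = 0.5 both equal √0.75 = 0.866, or 13% narrower.

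For the small sample, 400,000 trials per correlation were simulated at 18 per arm, adjusting only when a baseline t-test gives p < 0.05 (an assumed trigger, met in 5% of trials). Change in the 95% CI width for a single-visit arm difference when adjustment is always made:

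| r | Plan analyses follow-up value | Plan analyses change |
|---|---|---|
| 0.1 | 0.7% wider | 24% narrower |
| 0.3 | 3% narrower | 18% narrower |
| 0.5 | 12% narrower | 12% narrower |
| 0.7 | 27% narrower | 6% narrower |

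Type I error under the plan's rule runs from 0.050 down to 0.036 (follow-up values) and from 0.038 to 0.046 (change), so the rule is not anti-conservative. A baseline main effect alone leaves the complete-data group-by-time contrasts unchanged; the gain is in the arm difference at a visit.

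**The case against.** - **The inflation is small and conditional.** This stands. It is 0.6 to 1.3 points with complete data, and only with an ordinary F. The plan's silence is not a choice of that reference, but a chi-square reference would be worse, and nothing in the text supplies a correction.
- **A three-visit, 2-df test is one reading.** The stated hypothesis is about level, and a single contrast runs at 5.6%. Fair. In the other direction, the endpoint list also includes months 3 and 6; with all five visits and unstructured covariance the ML size is 7.9% at 20 per arm and 8.3% at 18.
- **The dropout runs are not the planned analysis.** The plan says "As missing data are inevitable in a longitudinal study" and turns to multiple imputation or pattern-mixture models, neither of which was simulated. This stands: the dropout figures apply to direct likelihood only.
- **Dropping AIC/BIC selection is partly preference.** Largely conceded. REML with Kenward-Roger after selection is already within about half a point of 5%.
- **The baseline may already enter by subtraction, and the gain is hypothetical.** If the outcome is change, what remains is the efficiency of covariate adjustment over change scores. The correlation is unknown and may be low, because all patients receive induction after the baseline draw. The Treg endpoint also already has stated power of 0.99, while graft function gains nothing. These points limit the benefit. They do not make a rule without a criterion preferable to a prespecified covariate that costs under 1% in width at worst.

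**Conclusion.** Both points hold, as modest but worthwhile corrections.

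On (a), given an ordinary F reference, the three-visit group-by-time test runs at about 6% rather than 5%: with unstructured covariance and 18 per arm, a reported p of 0.05 corresponds to about 0.063. Under the assumed dropout and direct likelihood it is higher. REML without a degrees-of-freedom correction does not fully repair it.

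On (b), the loss is one of precision and prespecification, not of type I error. Its size depends on an unknown correlation and on whether the Treg outcome is a follow-up value or a change, which the plan leaves open.

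The closed-form sizes are exact for complete normal data. The selection, dropout and covariate figures rest on the assumptions stated with them.

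**What to change.** Replace the estimation and covariate text with one paragraph that:

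1. fits the primary mixed models by REML with Kenward-Roger degrees of freedom (DDFM=KR);
2. prespecifies unstructured covariance for the 12-, 24- and 36-month model in place of AIC/BIC selection (the least essential of these changes);
3. always includes the pre-randomisation value of the same marker, with its interaction with visit, in the Treg, T-cell and B-cell models, instead of the conditional rule;
4. states whether the Treg outcome is the follow-up value or the change from baseline (with item 3 in place the estimated arm difference is the same either way);
5. states whether the primary model is fitted to observed or imputed data, since the correction was checked only for the former.

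**Cost.** No new data and two procedure options. Intervals widen slightly and a few model degrees of freedom are used. If compound symmetry were true, the group-by-time test would have 78.0% power with unstructured covariance and Kenward-Roger, where a correctly sized compound-symmetry test has 80.0% (noncentrality 10.07; F on 2, 33 against 2, 68 df). If baseline and follow-up are nearly uncorrelated, the single-visit interval widens by less than 1%.

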**Study design**

**Renal Transplant Recipients:**

All recipients will receive the same induction immunotherapy at time of transplant. : Campath (30mg IV x1) will be administered at the time of surgery. Methylprednisolone (500 mg IV) will be administered on the day of transplant and on days 1 (250 mg IV), and 2 (125 mg IV) post-transplant. No further steroids will be given post-transplant unless indicated by the following medical conditions: acute renal allograft rejection, renal diseases necessitating the use of steroids, and other systemic diseases such as rheumatoid arthritis (RA), systemic lupus erythematosus (SLE), and asthma.

Maintenance immunosuppression is administered according to the 1:1 randomization at time of enrollment: 20 subjects will begin **standard dose tacrolimus and MMF (control arm)**

Tacrolimus will be initiated according to our practice. The dose will be adjusted from day 3 on to achieve a target whole blood trough concentration of 8 ng/mL to 10 ng/mL. From month 2 until Month 6, the target tacrolimus trough level will be reduced to 6 ng/mL to 8 ng/mL. After month 6, the target level will be reduced to 4 ng/mL to 8 ng/mL.

MMF dose will be initiated as 1 g b.i.d. (2 g/day). Adjustments should be made for adverse events including but not limited to gastrointestinal intolerance and a decrease in WBC. MMF trough or AUC shall not be used to adjust dosing.

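### Covariates enter the models only through chance baseline imbalance, and the pre-randomisation cell value, collected in every recipient, has no prespecified role

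*Combined protocol and SAP*

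**What the plan says.** The Statistical analysis section plans two longitudinal analyses, a repeated-measures ANOVA and a mixed model with random effects. Their stated aim is: "compare the trajectory change in graft function and proportion of regulatory T cells over 12, 24 and 36 months between the two experimental groups". It names no covariate and no baseline term. The one sentence on covariates is conditional on the arms proving unequal despite randomisation: where "baseline characteristics are found to be different between the two experimental groups, these variables will be entered as covariates in the statistical analysis". It gives no test, threshold or variable list. The same section also says "We will run univariate and bivariate analyses for all variables prior to our main analyses", using t-tests, F-tests and chi-square tests, but does not tie that screening to covariate selection.

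The Study design section (treatment-arm subsection) states "Blood samples will be obtained prior to randomization from all renal transplant recipients for baseline T and B cell functional activity"; the samples also serve to characterise the cell subpopulations. Later samples serve to study the "subpopulation of T cells in comparison with baseline levels"; no model is attached to that purpose. The same subsection lists the data taken at randomisation: demographics, cause of renal disease, "Transplant related information: donor age, histocompatibility and cross match data, viral serology", then, further along the same list, "history of acute rejection and delayed graft function, use of ACEI and/or ARB, level of renal allograft function", and proteinuria.

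The outcome scale varies. The Statistical analysis hypothesis concerns higher Treg numbers, the model concerns their proportion, and Sample size and power refers to percentage Treg change.

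**The concern.** In a randomised trial, a baseline difference between arms is chance. A rule that waits for one selects the variables most correlated with arm, whether or not they predict outcome. Entering such a variable inflates the variance of the treatment effect, with no gain unless it is also prognostic. A strongly prognostic variable that happens to be balanced stays out, and its precision gain is lost.

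For the cell endpoints, the natural prognostic candidate is the recipient's own pre-randomisation value. Because its role is unstated, the analyst could use the follow-up value alone, adjust for baseline, or take a change from baseline. These differ in precision, and the choice could be made after the results are seen. Depleting induction "will be administered at the time of surgery", between the baseline sample and every follow-up sample. The baseline-to-follow-up correlation may therefore be low, which is where a change score performs worst.

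**Working it through.** **Inputs from the documents.** 20 per arm, 10% attrition at 12 months, two-sided 0.05, at least 80% power, effect sizes d of 1.0 (graft function) and 2.0 (percentage Treg change), stated power 0.82 and 0.99 (Sample size and power). **Assumed:** a p<0.05 imbalance screen, all correlations (rho), 40% prevalence for binary items, and within-subject correlation r.

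**1. The plan's own figures.** 20 × 0.9 = 18 per arm. A two-sample t-test with noncentrality d × √(18/2) and 34 df gives power 0.830 at d = 1.0 and 0.9999 at d = 2.0. The stated 0.82 and 0.99 reproduce, for an unadjusted comparison.

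**2. Why selection on imbalance costs precision.** With one covariate, the variance of the adjusted difference is σ²(1 − rho²)[2/n + D²/Sxx], where D is the baseline difference between arms and Sxx the pooled within-arm sum of squares. If t is the baseline t statistic, D²/Sxx = (2/n) × t²/34.
- A covariate that only just triggers has t = 2.03, so t²/34 = 4.13/34 = 0.121. At rho 0 the standard error rises by at least √1.121 − 1 = 5.9%.
- A covariate chosen in advance has average t²/34 = 1/32 = 0.031. The standard error rises by √1.031 − 1 = 1.5%.

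**3. The rule with several non-prognostic items.** The Study design list has 13 items besides the cell values. Eight are clearly fixed before transplant: age, sex, race, cause of renal disease, donor age, histocompatibility, cross match and viral serology. Simulation at d = 1.0, single time point, every flagged item entered:

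| Items | Any item enters | Power, rule vs unadjusted | 95% half-width (SD), rule vs unadjusted |
|---|---|---|---|
| 8 (2 continuous, 6 binary) | 38% | 0.796 vs 0.828 | 0.698 vs 0.672 |
| 13 (5 continuous, 8 binary) | 53% | 0.782 vs 0.831 | 0.714 vs 0.671 |

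The widening is 0.698/0.672 = 1.04 and 0.714/0.671 = 1.06. If ten items each have rho 0.2, the loss shrinks to 0.834 − 0.818, under two points. Under the null, type I error with 13 items is 0.047-0.050.

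**4. The mean of the three planned visits.** Its variance is (1 + 2r)/3 of a single visit's.
- r = 0.5: variance 0.667. Power is 0.95 unadjusted, 0.93 with 8 items, 0.92 with 13.
- r = 0.7: variance 0.80. Power is 0.90 unadjusted, 0.87-0.88 with 8 items, 0.86 with 13.

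The loss is 2 to 4 points, and power stays above 80%.

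**5. When the cell baseline is prognostic.** Power at d = 1.0 (illustrative for a cell endpoint), rule vs always adjusting:
- rho 0: 0.827 vs 0.819
- rho 0.2: 0.828 vs 0.833
- rho 0.3: 0.834 vs 0.855
- rho 0.5: 0.835 vs 0.910

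**6. Three ways to use the baseline.** The 95% half-width in follow-up SDs is 0.67 unadjusted. A change score multiplies it by √(2(1 − rho)) if the SDs are equal. Adjustment multiplies it by √(1 − rho²) and adds the 1.5% from step 2.

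| rho | Unadjusted | Change score | Adjusted |
|---|---|---|---|
| 0 | 0.67 | 0.95 | 0.68 |
| 0.2 | 0.67 | 0.85 | 0.67 |
| 0.3 | 0.67 | 0.80 | 0.65 |
| 0.5 | 0.67 | 0.67 | 0.59 |

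If the baseline SD is half the follow-up SD, change score and adjustment are close: 0.66 vs 0.65 at rho 0.3, and 0.58 vs 0.59 at rho 0.5.

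**7. Choosing afterwards.** Taking the smallest p-value of the three analyses gives type I error of about 0.093, 0.093 and 0.102 at rho 0.3, 0.5 and 0.7.

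**The case against.** The best defence is that the consequences are small and rest on assumptions. No threshold is stated, so the p<0.05 screen is a reading of the plan. The larger losses need all 13 items to be screened and none to be prognostic. Some of those items (eGFR, proteinuria, delayed graft function) may describe a graft not yet in place if randomisation is at enrolment. The plan is longitudinal, and averaging visits leaves power well above target. All of this stands.

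A reader might infer that the rule takes graft function below the plan's 80% minimum. The documents do not support that as a general statement. It appears only at a single time point, and step 4 shows that it fails for the mean of three visits. If the planned contrast is group by time instead, neither calculation applies directly.

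A reader might also infer that the plan commits to change scores. It does not. The hypothesis concerns levels, comparison with baseline is given as a purpose of sampling, and percentage Treg change is a label in the power statement. If the d of 2.0 is already on a change scale, the half-widths in step 6 do not map onto it. What stands is that the plan does not rule a change score out.

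Finally, if induction makes rho low, adjustment gains little: below about 0.2 it gains nothing or costs slightly. That limits the benefit, but it does not justify selecting covariates on imbalance.

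**Conclusion.** The point holds as a modest improvement to the analysis plan. That imbalance is the only route for covariates is inferred from the absence of any other rule. Under the assumed screen on non-prognostic items, the rule widens the interval by about 4-6% and costs about 2-5 power points at d = 1.0; the loss is about one point if many items are mildly prognostic. Where the cell baseline is prognostic, the rule recovers almost none of the gain from always adjusting. At the plan's Treg effect of 2.0, power is at least 0.98 under all three uses of the baseline, so the gain there is precision only.

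The rule should not be read as inflating type I error: applied as written, it holds the level or falls slightly below it. The inflation in step 7 arises only if the analysis is chosen after the results are seen. The plan does not propose that, but its silence on the baseline leaves room for it. Nor are the stated power figures wrong. Confidence is medium, because neither rho nor the trigger is given.

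**What to change.** Delete the imbalance-triggered sentence. In each cell-endpoint model, always include the pre-randomisation value of the same subset, with a baseline-by-visit term. State that this is the single primary analysis and that it takes the place of change scores. For graft function, prespecify either no covariate or a short named list of variables fixed before randomisation, which excludes current-graft eGFR, proteinuria and delayed graft function. Report baseline imbalance descriptively.

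This is a change of wording and needs no new data. It uses one degree of freedom per cell model plus the baseline-by-visit terms. If the baseline proves not to be prognostic, the interval is 1-2% wider than unadjusted and power at d = 1.0 falls from 0.83 to 0.82.

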### **Population**

The study will be conducted at Northwestern University Feinberg School of Medicine/Northwestern Memorial Hospital, and subjects will be recruited during visits to the Comprehensive Transplant Center. We plan to enroll and randomize recipients and their respective donors until 40 recipients have started the study drug to which they were randomized. As of January 2014, 3 recipients randomized to the experimental arm and 1 randomized to the control arm were withdrawn prior to dosing due to surgical complications. Replacement pairs will be enrolled, bringing the prospective enrollment to a minimum of 44 donor/recipient pairs (at least 88 total subjects).

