### **Sample size and power**

[figure not shown]
We calculated our sample power for the two primary endpoints based on our clinical experience and small pilot data. Using a two-tailed  $\alpha$  of 0.05, the anticipated effect sizes corresponding to each specific aim between the two treatment arms were calculated using a minimum of 80% statistical power and assumed 10% attrition at 12 months.

For the sample size of  $n= 20$  in each group, the proposed study will have a power of 0.82 and 0.99 to detect effect size of 1.0 and 2.0 for graft function and % regulatory T cell change, respectively, between the two treatment arms. Because this is a pilot study, we do not consider the statistical power of secondary outcomes; It is anticipated that a much larger sample size will be needed in order to achieve statistical power for the secondary endpoints in this proposed study.

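### Logistic and Cox models are planned for rejection, graft failure and death in about 20 recipients per arm, with no method for zero or very few events

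*Combined protocol and SAP*

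**What the plan says.** The Statistical analysis section covers the secondary event endpoints in one sentence: "we will use logistic regression, Kaplan-Meier method, and Cox proportional hazards models to analyze time-to-event outcomes". The outcomes it lists are acute rejection, graft failure and death, and the same section wants incidence at 12, 24 and 36 months. It names no exact, penalised or other sparse-event method. It also lets any baseline variable that turns out imbalanced enter the analysis as a covariate, without limiting how many.

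The size is fixed under Population ("We plan to enroll and randomize recipients and their respective donors until 40 recipients have started the study drug") and under Study design ("Maintenance immunosuppression is administered according to the 1:1 randomization at time of enrollment"), which gives 20 per arm.

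Sample size and power gives figures only for the two primary endpoints: "the proposed study will have a power of 0.82 and 0.99 to detect effect size of 1.0 and 2.0", with "assumed 10% attrition at 12 months". Of the remaining endpoints it says: "It is anticipated that a much larger sample size will be needed in order to achieve statistical power for the secondary endpoints". No event rate for rejection, graft loss or death appears anywhere.

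**The concern.** Standard logistic and Cox models estimate the treatment ratio by maximum likelihood. When one arm has no events, the likelihood keeps increasing as the log ratio moves towards infinity, so no finite estimate exists. Software then prints a large arbitrary number with an enormous standard error. With 20 per arm and an uncommon event, this is a foreseeable outcome, and the plan does not say what would then be reported.

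There is a second, separate difficulty. Logistic regression needs each recipient's event status at a fixed time. A recipient who leaves event-free at month 14 has no known status at months 24 or 36. Kaplan-Meier and Cox use that recipient's time at risk; logistic regression cannot. Yet the plan lists it for outcomes that it itself calls time-to-event.

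Rejection matters most here. The rationale for the trial is that reduced tacrolimus exposure with everolimus can still control alloreactivity, so readers will look for an honest interval on rejection even in a pilot.

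**Working it through.** **The plan's own figure.** The only stated powers are 0.82 and 0.99, for the primary endpoints. Ten percent attrition leaves 20 × 0.9 = 18 per arm. A two-sided two-sample t-test at 0.05 has 34 degrees of freedom and, for effect size 1.0, noncentrality 1.0 × √(18/2) = 3. Power is 0.830, close to the stated 0.82. For effect size 2.0 it is 0.9999, consistent with 0.99. These figures reproduce but say nothing about the event endpoints.

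**Inputs for the event endpoints.** The 20 per arm comes from Population and Study design. The risk p by the time of analysis is not in the documents. It is assumed here, equal in both arms, and varied.

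**Chance of a zero-event arm.** For one arm, q = (1 − p)^20. For at least one of two arms, P = 1 − (1 − q)². At p = 0.05, q = 0.95^20 = 0.358 and P = 1 − 0.642² = 0.588. The last column repeats this with 18 per arm.

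| Assumed risk p | q, 20 per arm | P(at least one zero arm), 20 per arm | Expected events in 40 (40p) | P, 18 per arm |
|---|---|---|---|---|
| 2% | 0.668 | 0.89 | 0.8 | 0.91 |
| 5% | 0.358 | 0.59 | 2 | 0.64 |
| 10% | 0.122 | 0.23 | 4 | 0.28 |
| 15% | 0.039 | 0.08 | 6 | 0.10 |
| 20% | 0.012 | 0.02 | 8 | 0.04 |

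Setting P = 0.5 gives q = 1 − √0.5 = 0.293 and p = 1 − 0.293^(1/20), about 6.0% (about 6.6% with 18 per arm). Above that risk, a zero-event arm is the less likely outcome.

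The equal-risk assumption can be relaxed using P = 1 − (1 − q₁)(1 − q₂). Risks of 5% and 10% give 0.44; risks of 10% and 20% give 0.13.

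**Three endpoints together.** If the endpoints are treated as independent, which is a simplification, risks of 10%, 5% and 5% give 0.87 for a zero arm in at least one of them. Risks of 20%, 10% and 5% give 0.69.

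**What a zero arm does.** Take 0/20 against 2/20.
- Ordinary logistic log odds ratio: −4.0, −9.0 and −14.0 after 5, 10 and 15 iterations, with standard errors of about 5, 61 and 738. It does not converge.
- Ordinary Cox log hazard ratio: about −61, with a standard error of about 1.6 × 10¹³.
- Firth-type odds ratio (0.5 added to each cell): (0.5 × 18.5)/(2.5 × 20.5) = 0.18. The standard error of its log is √(1/0.5 + 1/20.5 + 1/2.5 + 1/18.5) = 1.58, giving a Wald 95% interval of 0.008 to 4.0. It is finite and honestly wide. Fisher's exact p is 0.49.

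**Without a zero arm.** The standard error of a log hazard ratio is roughly √(1/d₁ + 1/d₂), where d₁ and d₂ are the event counts. With 4 and 4 events it is 0.71, so the 95% limits are the estimate divided and multiplied by exp(1.96 × 0.71), about 4. With 1 and 1 events it is 1.41 and the factor is about 16. Each added covariate must be supported by the same 2 to 8 events.

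**The case against.** Several points on the other side are fair.

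- **Likelihood of a zero arm.** A reader might infer that zero-event arms are likely for all three endpoints. The documents do not support that. They give no rates, and the chance passes one half only below about 6% risk. Living-donor recipients with PRA below 20% might have graft loss and death that rare, but this is an assumption. Nothing places rejection below 6%; at 10% to 20% the chance is 23% to 2%, and imprecision is the main problem.
- **No usable interval.** This is also too strong. Kaplan-Meier is planned in the same sentence and survives a zero arm. The log-rank test stays finite when only one arm is empty, and a profile-likelihood interval keeps one finite limit. What fails is the point estimate and the Wald interval, and the plan does not commit to Wald intervals.
- **Unpenalised estimation is an inference.** The plan names model families, not estimators; its maximum-likelihood sentence concerns the mixed models for graft function and Tregs. The point is therefore an omission, not a stated error.
- **Loss to follow-up.** Compounding 10% a year gives 1 − 0.9³ = 27% by month 36, but the plan assumes 10% at 12 months only, in a power calculation for other endpoints. Recipients are followed routinely at the centre, so a missed research sample need not mean unknown graft or vital status. The plan also offers multiple imputation and pattern-mixture models, so lost recipients would not necessarily be dropped or counted as event-free. It does not say, however, how event status would be imputed. Some incomplete follow-up is foreseeable from the text: certain infections can end participation. Study duration also expects no more than two years after the last enrolment, against 36 months of follow-up in Study design.
- **Pilot status.** The plan disclaims power for secondary endpoints, and no decision rule depends on these ratios. That limits the consequence. It does not make an infinite ratio reportable, and the plan still applies two-sided 0.05 tests throughout.

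The chi-squared test given for categorical variables is no fallback: 2 to 8 events in total mean 1 to 4 expected per arm, below the usual minimum of 5.

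**Conclusion.** The point stands in a limited form. The plan names logistic and Cox models for sparse events in about 20 recipients per arm and gives no exact or penalised method. A zero-event arm would leave the maximum-likelihood ratio infinite. Its chance is 59%, 23% and 8% at assumed risks of 5%, 10% and 15%, equal in both arms. For any endpoint between 5% and 20% risk, about 2 to 8 events in total make the ratio unstable whether or not an arm is empty, and unrestricted covariates make it worse. Separately, logistic regression is unsuitable wherever follow-up is incomplete; how much would be incomplete cannot be sized from the documents.

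This is a cheap improvement to secondary, pilot-level analyses. It does not touch the primary endpoints, and it does not show that the rejection comparison will fail.

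**What to change.** Replace the sentence on secondary event endpoints with a short pre-specified set, for each of rejection, graft failure and death:

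1. Event counts per arm with exact confidence intervals, and Kaplan-Meier estimates at 12, 24 and 36 months. Zero in 20 then reads as 0% with an exact two-sided 95% upper limit of 1 − 0.025^(1/20) = 16.8%.
2. For any risk difference when an arm has no events, an exact or score-type interval. Greenwood's variance is zero in such an arm, so the usual Kaplan-Meier interval would ignore its uncertainty.
3. An exact or permutation log-rank test to compare arms.
4. If a hazard ratio is reported, Firth-penalised Cox with profile-likelihood limits and treatment as the only covariate.
5. No logistic regression where follow-up is incomplete.
6. A statement that these results are descriptive.

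The cost is a few lines of SAP text. The Firth penalty is an option in the SAS proportional-hazards procedure; confirm it for the version the plan names. The downside is that wide intervals are shown openly, which is the accurate picture at this sample size.
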